#### 4.2. Pilot sites description

- Italy: In Italy the end-user partner will be recruited from the Geriatrics Operating Unit of IRCCS INRCA. The research team includes multidisciplinary professional personnel that will have the possibility to meet end-users and their families to present the project and the modalities of possible participation. It will be responsibility of the research group to give technical support with the use of the TransCare technological ecosystem and take track of clinical flux of data acquired from each participant to correctly archive it and analyze it afterwards. End-users involved in pilot trial will first be screened by the appropriate physician or nurse for evaluation of clinical and physical/cognitive inclusion criteria and eventual recruitment for the TransCare project. The typical inpatient that is hospitalized in the IRCCS INRCA geriatrics department is an older adult, frail and often multi-morbid, who access the hospital for a series of conditions that fall in the acute infectious processes (urinary, biliary tract infection etc.) or cardiac sphere (chronic heart failure).
- Norway: In Norway, patients will be recruited from the municipal care services in collaboration with the local hospital (Sørlandet sykehus avd. Flekkefjord). The municipal services office serves as the single point of contact for all patients and is notified by the hospital of all potential new patients shortly after admission. The project multidisciplinary team will work closely with the municipal services office to identify and recruit patients. When a potential patient is identified, the project multidisciplinary team will meet the patient and their family to present the project. Screening for cognitive and physical inclusion criteria will be a shared responsibility between the hospital and municipal multidisciplinary teams. Home health services will provide technical training on the equipment to the patient and will also be responsible for the daily follow-up. Home health will respond to measurements and forms that trigger alarms. The typical patient receiving care in the FAR municipality is an older, frail patient with chronic illness, infections, or those requiring postoperative rehabilitation.

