# 6 Study endpoints

### 6.1. Primary endpoint

The primary endpoint of the study is constituted by the reduction of the incidence of 30-days rehospitalization rate, supporting the self-management of the patients through an innovative remote monitoring system. It will be accessed by checking if the older adult is readmitted in the healthcare facility at the end of the 30 days trial period.

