# 8 Procedure

# 8.1. Recruitment (R) and Baseline Evaluation (TO)

Recruitment and experimentation procedures are the same among the three European pilot sites. Patient will be enrolled from the operative unit/facility department, listed below:

- Geriatrics Acute Care Ward of IRCCS INRCA, in the Ancona branch, according defined inclusion criteria.
- Medical and Geriatric Departments at Sørlandet Hospital Health Trust, Flekkefjord, and the allocation of services department of municipality of Farsund according to defined inclusion criteria.
- Cardiology Department of the 'Niculae Stancioiu' Heart Institute, in Cluj-Napoca, according to the defined inclusion criteria.

During the recruitment phase (R), i.e., prior to discharge or within 3 days of discharge, general information will be collected about the subjects, particularly health status and cognitive condition. MMSE will be administered to gain a cognitive level framework, the CFS to evaluate frailty and SPPB to access physical condition.

The investigator will contact (by mail, telephone or physically) the participant to define his availability with a view to setting up the research project at home and will access his/her signed consent. When recruitment is complete, the investigator will randomize the participants into two groups: control group and experimental group. The allocation is done in an alternating randomized manner (ABAB) according to the order of inclusion of the participants. Participants in the experimental group will receive the digital platform already installed in a tablet (Table 4), or alternatively, they will use their own smartphone. In this case, they will be helped with the installation of the application and advised on how to use it. Furthermore, they will receive a set of medical/non-medical devices as reported in Table 2 and Table3. Participants in control group will not be assigned any type of technology but will simply be checked whether they will be re-hospitalized at the end of 30, 60, or 90 days.

At the staring of the experimentation, baseline evaluation (T0) is conducted directly at the hospital or at patient's home according to specific local needs of each end-user partner. The scales included Sociodemographic questionnaires, ATDPA-C, EQ-5D-5L VAS, SF-12 and eHEALS, will be administered.

The participant belonging to experimental group will receive training sessions about the digital platform and the medical/non-medical device utilization.

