During the first month of experimentation, the participant belonging to the experimental group will be invited to use the devices in the way he/she wishes. In any case, participants will not be obliged to manipulate the devices.

In addition, during the experimentation phase, participants will be contacted weekly to inquire about the utilization experience and their feelings about the activity and, possibly, offer technical help when needed.

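### Weekly staff contact appears to go to the experimental arm only, so a lower readmission rate would be the effect of system plus training plus contact, not of the monitoring system alone as the endpoint is worded

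*Protocol*

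**What the plan says.** **Contact by arm.** Section 8.1 gives the experimental group the platform, the devices, help with installation and training. It closes by saying that "during the experimentation phase, participants will be contacted weekly to inquire about the utilization experience and their feelings about the activity" and that technical help may be offered. For the other arm it says: "Participants in control group will not be assigned any type of technology but will simply be checked whether they will be re-hospitalized", at 30, 60 and 90 days.

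**What the effect is credited to.** Section 6.1 defines the primary endpoint as a reduction in 30-day re-hospitalization, "supporting the self-management of the patients through an innovative remote monitoring system". Section 9 sizes the trial on a 14.1-point reduction attributed to remote monitoring. Section 3.1 is broader: it speaks of a new care pathway, but the components it lists are medical devices, an activity tracker and a platform.

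**Sites.** Section 8.1 states: "Recruitment and experimentation procedures are the same among the three European pilot sites". Section 4.2 says of Norway: "Home health services will provide technical training on the equipment to the patient and will also be responsible for the daily follow-up". It adds: "Home health will respond to measurements and forms that trigger alarms". Section 5 says that the operator sees only whether the technology works, does not interpret clinical data, sends no emergency alert, and is not there to monitor continuously.

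**Ascertainment.** Section 8.2 has re-hospitalization checked in both arms at 30 days. It then limits the full T1 evaluation, including clinical resource utilization, to the experimental group. The T1 resource-use form in the Appendix has a block for hospital admissions with dates and diagnosis.

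**The concern.** Between discharge and day 30 the two arms differ in more than the technology. One arm has training and someone who calls each week to ask how things are going; the other has neither. The protocol's own introduction names follow-up and psychological support among transitional-care interventions, and lack of timely follow-up among the post-discharge problems behind readmission. By that reasoning the contact could itself affect the outcome. If the trial is positive, the endpoint as worded invites a conclusion about self-monitoring technology that the comparison cannot isolate.

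Two related matters affect how the result is read. If follow-up and alarm handling differ in Norway, the package is not the same at every site. If one arm has an extra form on which admissions are recorded, and the protocol does not say which source decides the endpoint, readmissions could be captured differently by arm.

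**Working it through.** **1. Which arm is contacted weekly.** The sentence says only participants. Its content (experience of use, technical help) presupposes a device. The paragraph before it concerns the experimental group, and controls have nothing to use. Set beside "will simply be checked whether they will be re-hospitalized at the end of 30, 60, or 90 days", the natural reading is experimental arm only. This is an inference, and no sentence contradicts it.

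**2. How much contact.** Inputs: weekly contact (8.1), 105 experimental patients (section 7), recruitment up to 3 days after discharge (8.1).
- Counted over the full window: floor(30/7) = 4 by day 30, floor(60/7) = 8 by day 60, floor(90/7) = 12 by day 90.
- Starting 3 days after discharge: floor(27/7) = 3 by day 30.
- Over the arm by day 30: 105 × 3 = 315 to 105 × 4 = 420. Controls: none scheduled between checks.

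**3. The planned effect size and what it is attributed to.** Inputs from section 9: 5.2% against 19.3%, two-sided Fisher's exact test, α = 0.05, power 0.85, 103 per arm. Power is the sum over all outcomes (x, y) of Bin(x; n, 5.2%) × Bin(y; n, 19.3%) for which the Fisher p-value is at most 0.05.
- n = 102: 84.9%; n = 103: 85.2%; n = 105: 86.0%.

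The stated 103 per arm is reproduced exactly, so the sample size is not in question. All 14.1 points are assigned to remote monitoring.

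**4. Illustration of what attribution means.** Assumption, not in the documents: a share s of the 14.1 points comes from staff contact. Controls with matched contact would then have a rate of 19.3 − s × 14.1. Power for the remaining difference from 5.2%, at 103 per arm:

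| s | matched control rate | power |
|---|---|---|
| 25% | 19.3 − 3.525 = 15.775% | 63.9% |
| 50% | 19.3 − 7.05 = 12.25% | 34.7% |
| 75% | 19.3 − 10.575 = 8.725% | 10.9% |

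The documents give no basis for choosing s, and s may be zero. The table shows only that a design powered for the package need not be powered for the system's own contribution.

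**5. Sites side by side.** Section 8.1: the same procedures everywhere. Section 4.2: in Norway, daily follow-up and a response to alarms. Section 5: no interpretation of clinical data and no emergency alert. Norway supplies 40/105 = 38% of the experimental arm (Table 1). The three statements do not fit together as written.

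**6. Ascertainment side by side.** Section 8.2 has the yes/no check in both arms, but the questionnaire that lists admissions in the experimental arm only. Section 6.1 says that readmission is checked without naming the source.

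**The case against.** The strongest reply is that this is a pragmatic trial. User support is an ordinary part of putting home technology into the hands of people aged 65 and over, some with MMSE 18 to 25, and section 3.1 already speaks of a care pathway. Comparing the supported system with no system is a valid question. That stands, and it is why the remedy is wording and not matched contact in controls. It does not rescue sections 6.1 and 9, which name the monitoring system alone.

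It is also fair that nothing in the documents shows that usability calls reduce readmission. The concern is that the design cannot separate the two, not that the calls are known to work.

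Some site variation is declared openly, such as the choice of devices and the cameras and personal alarms used only in Norway (5.1). Daily follow-up and alarm response are described for Norway in 4.2, but they are not reconciled with 8.1 or section 5.

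A reader might go further in three ways that the text does not support:
- *That Norway's daily follow-up is the weekly call under another name, or means a contact every day.* Section 4.2 describes a different service, names no arm and does not define a contact, so no count can be drawn from it.
- *That 8.1 contradicts itself on contact.* Its statements on the two arms are compatible.
- *That weekly calls bias detection because staff hear of admissions sooner.* The endpoint is a yes/no at day 30 checked in both arms, and earlier knowledge does not change that answer. The calls are not said to ask about admissions.

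**Conclusion.** The point holds as one about attribution. The comparison estimates the effect of system, training and scheduled staff contact against usual care. A lower readmission rate cannot be credited to the monitoring system alone. It would be wrong to infer that a positive result is uninterpretable: the package contrast remains valid and the planned power for it is as stated.

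The conclusion rests on reading the weekly contact as confined to the experimental arm, and on no contact being scheduled for controls between checks. The size of any bias in a claim about the system alone cannot be derived from the documents.

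The site statements need reconciling whatever is decided about attribution, since they concern 38% of the experimental arm. On ascertainment, the text shows a possibility of unequal capture, not that it will happen. The whole should be corrected before analysis; it does not call for a change of design.

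**What to change.** 1. In 3.1 and 6.1, define the compared intervention as the monitoring system plus training and scheduled staff contacts, and word the conclusion as the effect of that package against usual care. Carry the same wording into section 9, and name the arm in the weekly-contact sentence of 8.1.
2. Reconcile 4.2, section 5 and 8.1 so that follow-up and alarm handling at each site are stated once, or declared as a site difference. Which rule applies is for the sponsor and investigators to decide.
3. State that readmission in both arms is taken from the same source at the same 30-, 60- and 90-day check, and not from the weekly contacts or from a form given to one arm only.

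This is protocol wording, with no added patients or visits. The cost is a slightly narrower claim: the package, not the technology by itself.

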## 8.2. First Intermediate Evaluation (T1 at 30 days)

Both for the experimental and control group, participants will be checked firstly if they were re-admitted in the hospital after 30 days of system utilization.

Only for the experimental group, after 30 days of system utilization, patients is evaluated or at home or at hospital. Participants will be evaluated on physical condition using the SPPB, quality of life through the VAS,

usability of platform and system using SUS. Clinical resource utilization, self-management improvement and effectiveness of the system will be accessed by administering questionnaires and interviews. Additionally, at T1 endpoint, the participants will be assisted by investigator in case of problem with system.

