# 7 Protocol

For this pilot study, 210 older adults will be enrolled. The participants will be randomized into 2 groups, respectively 105 cases and 105 controls. The randomization technique based on a single sequence of random assignments is used

A summary of all data collected and when these are collected is provided in Table 5. All scales used are validated in all the national languages of each end-user partner (Italian, Norwegian and Romanian) and suitable for administration for the patients recruited in the study. A complete list of scales are attached as Appendix to the present deliverable.

Scale(s)	R	то	T1	Т2	Т3
Socio-demographic and Anamnesis (Check-list)	$\checkmark$				
MMSE (cognitive)	$\checkmark$				
Short Physical Performance Battery (physical)	$\checkmark$		$\checkmark$	$\checkmark$	$\checkmark$
Clinical Frailty Scale (Frailty)	$\checkmark$				
30-days Rehospitalization rate (y/n)			$\checkmark$		
60-days Rehospitalization rate (y/n)				$\checkmark$	
90-days Rehospitalization rate (y/n)					$\checkmark$
ATDPA – C (Technology attitude)		$\checkmark$			
EQ-5D-5L (only VAS scale) (quality of life)		$\checkmark$	$\checkmark$	$\checkmark$	$\checkmark$
SF-12 short form (4 weeks recall period) ( impact of health in everyday life)		$\checkmark$	√		~
Clinical resource utilization			$\checkmark$	$\checkmark$	$\checkmark$
SUS (Usability of dashboard)			$\checkmark$		$\checkmark$
eHEALS scale (ehealth literacy)		$\checkmark$	$\checkmark$		$\checkmark$
Semi-structured interview on self-management improvement, usability and effectiveness of the system			√		$\checkmark$

Table 5 Clinical assessments and scales divided by different evaluation times

The **Mini Mental State Examination (MMSE)** [22] is a neuropsychological test used to assess cognitive function and detect cognitive impairment; it is particularly useful for monitoring the development of dementia and assessing the cognitive status of patients in clinical settings. Consisting of 30 questions, the test assesses five areas: orientation, registration, attention and computation, recall, language and visuo-constructive skills. The maximum score is 30, with scores below 24 indicating possible cognitive impairment.

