## 8.3. Second Intermediate Evaluation (T2 at 60 days)

Both for the experimental and control group, participants will be checked by investigator firstly if they were re-admitted in the hospital after 60 days of system utilization. The investigator will conduct interview for clinical resource utilization and evaluate level of quality of life through VAS and physical condition using the SPPB.

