## 8.4. Final evaluation (T3 at 90 days)

At the end of the trial, both experimental and control group participants are checked if they went into a rehospitalization after 90 days of system utilization. The investigator will conduct interview for clinical resource utilization, self-management improvement and effectiveness of the system by administering questionnaires and interviews, along with an evaluation of the level of quality of life through VAS and of the physical condition using the SPPB. Moreover, the investigator will evaluate usability of platform and system using SUS, the health-related quality of life using the SF-12 and the eHealth literacy using the eHEALS.

Finally, the devices including tablet, medical and non-medical devices will be withdrawn.

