- Data collected by the researchers: The first step of the data analysis will deal with the description of • the sample. Continuous variables will be reported as either mean and standard deviation or median and interquartile range based on their distribution (assessed using Kolmogorov-Smirnov test). Categorical variables will be expressed as an absolute number and percentage. Comparison of baseline measurements between groups will be evaluated by unpaired t-test (for normal distribution), Mann-Whitney U tests (for non-normal distribution), or Chi-Square tests (for categorical variables). Within each group, independent and dependent variables will be compared between the pre- and post- conditions using the same tests as appropriate. The treatment effect on the outcome variables will be evaluated by using repeated measures ANOVA, to compare the changes over time in the outcome measures between the intervention group and the control group. Moreover, a linear regression model on the outcome variation between baseline and follow-up will be estimated to evaluate the effect of the treatment adjusted for all potential confounders. Descriptive statistical analyses will be performed on the quantitative data with SPSS or Rstudio. All data acquired in the trial will be analysed directly by the research centres involved in the project consortium. Monitored data will be used as input to the ML-based post discharge analytics for training and inference processes allowing for the prediction of different parameters among patients involved in the experimentation. The ML component will determine insights that can be used as support by medical professionals to identify the problems that require proactive intervention. Work will be done on anonymized data and not on personal data, and the AI model will not interact for the testing phase with the end user, be it the patient or the practitioner. The practitioners can only access the results of the ML inference for their remotely monitored patients and to visualize the results in order to support their decisions regarding patients' treatment.

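### Control-arm scale assessments are excluded at 30 days and contradictory at 60 and 90 days, although section 9 plans a between-group comparison of change

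*Protocol*

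**What the plan says.** The Protocol describes control-arm follow-up in five places.

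- **Section 8.1:** controls receive no technology and "will simply be checked whether they will be re-hospitalized at the end of 30, 60, or 90 days". No scale is mentioned for their follow-up. The recruitment SPPB and the T0 scales are not limited by arm.
- **Section 8.2 (T1):** the readmission check covers both arms. The next paragraph begins "Only for the experimental group, after 30 days of system utilization, patients is evaluated or at home or at hospital" and continues "Participants will be evaluated on physical condition using the SPPB, quality of life through the VAS", followed by SUS, resource utilization and interviews.
- **Section 8.3 (T2):** after a readmission check in both arms, "The investigator will conduct interview for clinical resource utilization and evaluate level of quality of life through VAS and physical condition using the SPPB". No arm is named for these.
- **Section 8.4 (T3):** the same pattern, with SUS, interviews and "the health-related quality of life using the SF-12 and the eHealth literacy using the eHEALS" added.
- **Section 7, Table 5:** instruments are ticked by visit only.

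Section 9 plans a repeated measures ANOVA "to compare the changes over time in the outcome measures between the intervention group and the control group", and a linear regression on change from baseline to estimate the treatment effect.

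**The concern.** The analysis in section 9 needs the same scales in both arms at the same visits, and sections 8.1 and 8.2 do not provide them. Section 6.2 makes improved quality of life and physical performance a secondary endpoint, and sections 3.2 and 6.2 include resource use. Section 1 describes patients who leave hospital still clinically vulnerable, so some change in SPPB and self-rated health after discharge would be expected with or without the technology. Without concurrent control measurements, that recovery cannot be separated from a treatment effect.

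This is a matter of data collection. A later statistical analysis plan cannot recover assessments that were never made, and three sites reading these sections could reasonably collect different control data.

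**Working it through.** **1. The plan's own figure.** The only sample-size calculation is for 30-day readmission. Section 9 gives 19.3% (control) against 5.2% (intervention), a two-sided Fisher's exact test, α = 0.05, power 0.85 and 103 per arm. Exact power is the sum over all pairs (i, j) of Bin(i; n, 0.193) × Bin(j; n, 0.052), counting pairs with Fisher p ≤ 0.05.

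- n = 102 per arm: 0.8494
- n = 103 per arm: 0.8516
- n = 105 per arm (planned enrolment): 0.8598

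The stated 206 reproduces. It concerns readmission only, which is checked in both arms, so this point does not touch it.

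**2. Size of the control arm.** From Table 1: 50 + 15 + 40 = 105 controls of 210, and 105/210 = 50%.

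**3. Control measurements after baseline, under each reading.** The ticked visits are those in Table 5.

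| Instrument | Baseline | Ticked follow-up visits | Controls if 8.1 governs | Controls if 8.3 and 8.4 cover both arms |
|---|---|---|---|---|
| SPPB | R | T1, T2, T3 | 0 of 3 | 2 of 3 (T2, T3) |
| EQ VAS | T0 | T1, T2, T3 | 0 of 3 | 2 of 3 (T2, T3) |
| SF-12 | T0 | T1, T3 | 0 of 2 | 1 of 2 (T3) |
| eHEALS | T0 | T1, T3 | 0 of 2 | 1 of 2 (T3) |
| Clinical resource utilization | none | T1, T2, T3 | 0 of 3 | 2 of 3 (T2, T3) |

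At T1 both readings give zero for controls, because 8.1 and 8.2 agree there.

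**4. A second mismatch at T1.** Table 5 ticks SF-12 and eHEALS at T1, but section 8.2 names neither, for either arm.

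**5. Resource use.** There is no measurement at R or T0, so it can support a comparison between arms but not a change from baseline, whatever is done about controls. The form asks about visits, tests and care services over the past four weeks. At T2 that window opens on day 60 − 28 = 32, and at T3 on day 90 − 28 = 62. Neither reaches back into the first 30 days, so these items cannot be recovered for controls once T1 has passed. Hospital admissions are recorded over the whole time in the study, so a T2 or T3 form would capture first-month admissions.

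**The case against.** The strongest reply is that the authors wrote an explicit arm restriction at T1 and did not repeat it at T2 or T3, where both arms are named just before the scales are listed. On that reading the 8.1 sentence only contrasts controls with technology users, and baseline-to-T2 and baseline-to-T3 comparisons are available. This largely stands, and it rules out a reading that a reader might infer: that the between-group comparison is impossible at every visit. It does not settle the matter, because the T3 list also contains SUS and system effectiveness, which controls without the system cannot answer.

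Four other inferences go further than the documents.

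- *A repeated measures ANOVA that includes T1 would drop every control.* Section 9 specifies neither listwise deletion nor which visits enter the model.
- *Resource use has no comparator at all in the first month.* This is true of visits, tests and care services, but not of admissions if controls complete the T2 or T3 form.
- *Controls are already contacted at T1, so adding scales costs almost nothing.* The Protocol says only that readmission is checked. A records check would fit that wording.
- *The main result is at risk.* It is not, because readmission is checked in both arms.

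**Conclusion.** The concern holds in a limited form. Followed as written, the plan yields no control scale data at T1, so the section 9 comparison cannot be made at 30 days: 105 of 210 participants lack SPPB, EQ VAS and resource-use data there. At T2 and T3 the Protocol contradicts itself, and the usable control data range from none to the last column of the table above. First-month visits, tests and care services in controls would be permanently lost.

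This assumes that enrolment follows Table 1, and that the arm restriction opening the T1 paragraph in 8.2 governs all the scales listed in it. Section 8.1 supports that second assumption. Only secondary outcomes are affected, so the point ranks below anything that threatens the primary analysis. It should still be settled before follow-up starts, because the T1 loss cannot be repaired afterwards.

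**What to change.** 1. **Sections 8.1 to 8.4 and Table 5:** state for each arm which scales are taken at each visit, and add an arm split to Table 5. Reword the readmission-only sentence in 8.1 accordingly.
2. **T2 and T3:** state that controls complete the Table 5 instruments, namely SPPB, EQ VAS and Clinical Resource Utilization at both visits, and SF-12 and eHEALS at T3.
3. **T1:** take the questionnaires in both arms, by telephone if needed. Resolve whether SF-12 and eHEALS are taken at T1, since Table 5 ticks them and 8.2 omits them.
4. **SUS and the system interview:** keep for the experimental arm only, and say so.
5. **Section 9:** limit the between-group comparison to outcomes and visits measured in both arms (for example SPPB at T2 and T3 if no T1 control visit is made). Treat resource use as a between-arm comparison without a change score. Label any scale collected only in the experimental arm as within-group and not as a treatment effect.

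The cost is mainly wording. The one real addition is a short T1 contact for 105 controls, if the readmission check would otherwise be done from records. If the sponsor wants readmission only in controls, the last step still applies and the scale results become descriptive within one arm.
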